8.3.2. Reporting

Every SAE, regardless of suspected causality (eg, relationship to study drug or study procedure or disease progression), occurring after the subject has signed the ICF through the last study visit (or 30 days [+ 5 days] after the last dose of study drug, whichever is later), must be reported to the sponsor (or designee) within **24 hours** of learning of its occurrence, unless otherwise specified by the Protocol. Any SAEs occurring more than 30 days (+ 5 days) after the last dose of study drug should be reported to the sponsor or its designee only if the investigator suspects a causal relationship to the study drug.

Information about all SAEs is collected and recorded on the Adverse Event form of the eCRF. The investigator must assess and record the causal relationship of each SAE to the study treatment.

The investigator must also complete the Incyte Serious Adverse Event Report Form, in English, and send the completed and signed form to the sponsor or designee within 24 hours of becoming aware of the SAE. The investigator must provide a causality assessment, that is, assess whether there is at least a reasonable possibility that the SAE is related to the study treatment: suspected (yes) or not suspected (no). Refer to the Incyte Reference Guide for Completing the Serious Adverse Event Report Form.

The contact information of the sponsor's study-specific representatives is listed in the investigator manual provided to each site. The original copy of the SAE Report Form and the confirmation sheet must be kept at the study site.

Investigational site personnel/investigator (Japan) must report any new information regarding the SAE within 24 hours of becoming aware of the information in the same manner that the initial SAE Report Form was sent. Follow-up information is recorded on an amended or new SAE Report Form, with an indication that it is follow-up to the previously reported SAE and the date of the original report. The follow-up report should include information that was not provided on the previous SAE Report Form, such as the outcome of the event (eg, resolved or ongoing), treatment provided, action taken with study drug because of the SAE (eg, dose reduced, interrupted, or discontinued), or subject disposition (eg, continued or withdrew from study participation). Each recurrence, complication, or progression of the original event should be

reported as follow-up to that event, regardless of when it occurs. **Note for Japan:** Suspected expected deaths and life-threatening events will also be reported to the Pharmaceuticals and Medical Devices Agency (PMDA) as per local regulatory requirements. Collection and provision of safety information on phosphate binders: In case of an occurrence of an SAE that cannot deny the causal relation to phosphate binders, the investigator must report the event according to the procedure. These events will be reported to PMDA as per local regulatory requirements. The sponsor/designee will provide safety information of phosphate binders to the investigator and the head of the hospital, in accordance with Article 20, Paragraph 3 of the GCP Ministerial Ordinance.

If the SAE is not documented in the IB for the study drug (new occurrence) and is thought to be related to the sponsor's study drug, the sponsor or its designee may urgently require further information from the investigator for reporting to health authorities. The sponsor or its designee may need to issue an Investigator Notification (IN) to inform all investigators/all heads of study sites and investigators (Japan) involved in any study with the same drug that this SAE has been reported. Suspected Unexpected Serious Adverse Reactions (SUSARs) will be collected and reported to the competent authorities and relevant ethics committees in accordance with Directive 2001/20/EC, or as per national regulatory requirements in participating countries.

8.4. Emergency Unblinding of Treatment Assignment

Not applicable.

8.5. Pregnancy

Pregnancy, in and of itself, is not regarded as an AE unless there is suspicion that study drug may have interfered with the effectiveness of a contraceptive medication or method. When a pregnancy has been confirmed in a subject during maternal or paternal exposure to study drug, the following procedures should be followed in order to ensure subject safety:

- The study drug must be discontinued immediately (female subjects only; see Section 5.4 for the maximum permitted duration of study drug interruption).
- The investigator must complete and submit the Incyte Clinical Trial Pregnancy form to the sponsor or its designee within **24 hours** of learning of the pregnancy.

Data on fetal outcome and breastfeeding are collected for regulatory reporting and drug safety evaluation. Follow-up should be conducted for each pregnancy to determine outcome, including spontaneous or voluntary termination, details of the birth, and the presence or absence of any birth defects, congenital abnormalities, or maternal and/or newborn complications, by following until the first well-baby visit. Pregnancy should be recorded on a Clinical Trial Pregnancy form and reported by the investigator to the sponsor or its designee. Pregnancy follow-up information should be recorded on the same form and should include an assessment of the possible causal relationship to the sponsor's study drug to any pregnancy outcome, as well as follow-up to the first well-baby visit or the duration specified in local regulations, whichever is later. Refer to the Incyte Reference Guide for Completing the Clinical Trial Pregnancy Form.

Any SAE occurring during pregnancy must be recorded on the SAE report form and submitted to the sponsor or designee.

8.6. Warnings and Precautions

Special warnings or precautions for the study drug, derived from safety information collected by the sponsor or its designee, are presented in the [IB](#). Additional safety information collected between IB updates will be communicated in the form of Investigator Notifications (INs). Any important new safety information should be discussed with the subject during the study, as necessary. If new significant risks are identified, they will be added to the ICF.

8.7. Data Monitoring Committee

An independent Data Monitoring Committee (DMC) will be formed. The DMC will consist of qualified individuals who are not involved with the conduct of the study. The establishment, composition, roles, duties, and responsibilities of the DMC are addressed in the approved DMC charter.

8.8. Product Complaints

The sponsor collects product complaints on study drugs and drug delivery systems used in clinical studies in order to ensure the safety of study participants, monitor quality, and facilitate process and product improvements.

All product complaints associated with material packaged, labeled, and released by the sponsor or its designee will be reported to the sponsor. All product complaints associated with other study material will be reported directly to the respective manufacturer.

The investigator or his/her designee is responsible for reporting a complete description of the product complaint via email or other written communication to the sponsor contact or respective manufacturer as noted in the packaging information. Any AE associated with a product complaint should be reported as described in Section [8.1.2](#) of this Protocol.

If the investigator is asked to return the product for investigation, he/she will return a copy of the product complaint communication with the product.

9. STATISTICS

9.1. Study Populations

- Efficacy Evaluable: All subjects enrolled in the study who have a known FGF/FGFR alteration from sponsor's central laboratory and take at least 1 dose of study drug.
- Safety Evaluable: All subjects enrolled in the study who take at least 1 dose of study drug.
- Per Protocol: All subjects in the efficacy evaluable population who are sufficiently compliant with the Protocol.

9.2. Selection of Sample Size

Approximately 100 subjects who have FGFR3 mutations or fusions based on central genomics laboratory results are planned per each Cohort A-ID and Cohort A-CD. An agent used in the second line setting that has an ORR of 35% would be considered clinically meaningful. With the assumed rates of 35% for the intervention, a sample size of approximately 100 subjects per each Cohort A-ID and Cohort A-CD would provide a 95% confidence interval (CI) with a lower limit of > 25%, assuming 10% lost to follow-up. Approximately 40 subjects will be enrolled in Cohort B (all other FGF/FGFR alterations), which will provide > 80% chance of observing at least 6 responders if the underlying ORR is 20%.

Subjects enrolled without known FGF/FGFR alteration from the sponsor's central laboratory will not be included in the efficacy analyses and may be replaced.

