9.3. Level of Significance

All CIs provided will be at the 95% confidence level.

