9.4. Statistical Analyses

9.4.1. Efficacy Analyses

9.4.1.1. Primary Efficacy Analyses

The primary endpoint of the study is ORR in subjects with FGFR3 mutations or fusions based on the central genomics laboratory results and on a continuous dose regimen, defined as the proportion of subjects with best response (complete response or partial response) by RECIST v1.1 as assessed by a centralized radiological review committee. This analysis will be based on efficacy evaluable population. Subjects who do not have sufficient baseline or on-study response assessment information to be adequately assessed for response status will be included in the denominators in the calculation of ORR. The 95% CI for ORR based on exact method for binomial distribution will be calculated.

Objective response rate will also be analyzed based on per-protocol population as sensitivity analysis.

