### **3.2. Sample Size Considerations**

Approximately 100 subjects who have FGFR3 mutations or fusions based on central genomics laboratory results are planned per each Cohort A-ID and Cohort A-CD. An agent used in the second-line setting that has an ORR of 35% would be considered clinically meaningful. With the assumed rates of 35% for the intervention, a sample size of approximately 100 subjects per each Cohort A-ID and Cohort A-CD would provide a 95% CI with a lower limit of > 25%, assuming 10% lost to follow-up. Approximately 40 subjects will be enrolled in Cohort B (all other FGF/FGFR alterations), which will provide > 80% chance of observing at least 6 responders if the underlying ORR is 20%.

Subjects enrolled without known FGF/FGFR alteration from the sponsor's central laboratory will not be included in the efficacy analyses and may be replaced.

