### **7.2. Analysis of the Primary Efficacy Parameter**

#### **7.2.1. Primary Efficacy Analysis**

The primary endpoint of the study is ORR in subjects with FGFR3 mutations or fusions based on the central genomics laboratory results and on a continuous dose regimen, defined as the proportion of subjects with best response of CR or PR based on review of scans by an independent centralized radiological review committee per RECIST v1.1 ([Eisenhauer et al 2009](#)). Confirmation of CR and PR is required and documented in the Independent Review Charter. This analysis will be based on the efficacy evaluable population. Subjects who do not have sufficient baseline or on-study response assessment information to be adequately assessed for response status will be included in the denominators in the calculation of ORR. The 95% CI for the ORR will be calculated using the Clopper-Pearson method.

The ORR will also be analyzed based on the PP population as sensitivity analysis.

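### The sample-size statement for Cohorts A-ID and A-CD presents a 95% lower limit above 25% as assured, but at a true ORR of 35% the planned exact interval achieves it only about half the time

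*Protocol*

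**What the plan says.** Protocol section 9.2 starts from a rate, "With the assumed rates of 35% for the intervention", and plans roughly 100 patients for each of the two FGFR3 cohorts. Its conclusion is that this number "would provide a 95% confidence interval (CI) with a lower limit of > 25" percent. The allowance made for losses is given in the same sentence: "assuming 10% lost to follow-up". SAP section 3.2 repeats the conclusion ("would provide a 95% CI with a lower limit of > 25" percent), as does the protocol synopsis under Statistical Methods. None of the three gives a probability for Cohort A-ID or A-CD.

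The interval method is fixed. Protocol 9.4.1.1 states "The 95% CI for ORR based on exact method for binomial distribution will be calculated", and SAP 7.2.1 names it: "The 95% CI for the ORR will be calculated using the Clopper-Pearson method". Protocol 9.3 sets the level: "All CIs provided will be at the 95% confidence level". Protocol 9.4.1.1 and SAP 7.2.1 also keep subjects who cannot be adequately assessed for response in the ORR denominator.

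Three other places bear on the point:
- For Cohort B, Protocol 9.2 does give a probability tied to an underlying rate: a better than 80% chance of at least 6 responders among 40 if the ORR is 20%.
- The futility rule (Protocol 9.5, SAP section 9) is expressed through the probability of claiming an ORR above 25% at the final analysis.
- SAP 3.1 labels all analyses exploratory, and SAP 7.1 states no efficacy hypothesis.

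**The concern.** The sentence moves from an assumed rate to a confidence limit as though the assumed rate were certain to be observed. An assumption of this kind concerns the true rate. The observed rate will vary around it, and the lower limit will vary with it. Here the assumed rate lies almost exactly at the point where the lower limit crosses 25%, so the outcome is close to an even chance.

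This is the only quantitative justification for 100 subjects in each FGFR3 cohort, including A-CD, which carries the primary endpoint. A reader would conclude that a drug with the ORR the plan calls clinically meaningful will have a lower limit above 25%. The plan never gives the chance of that.

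**Working it through.** **Inputs.** True or observed ORR 35%, 100 subjects per cohort, target lower limit above 25% and 10% loss (Protocol 9.2); exact 95% interval, read as two-sided (Protocol 9.3 and 9.4.1.1, SAP 7.2.1). A 10% loss leaves 100 × 0.9 = 90.

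**Formulas.** For x responders of n, the Clopper-Pearson lower limit is the 0.025 quantile of a Beta(x, n − x + 1) distribution. The probability of clearing 25% is P(X ≥ r), where X is Binomial(n, p) and r is the smallest count whose lower limit exceeds 25%.

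**Step 1: reproduce the plan's figure, taking 35% as observed.**
- n = 100: 35/100 gives 25.7% to 45.2%.
- n = 90: 0.35 × 90 = 31.5 responders gives a lower limit of 25.2%, but 31.5 is not a possible count.

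So the stated figure reproduces when the observed rate equals the assumed rate.

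**Step 2: find the cut-off.**

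| Responders | Exact lower limit |
|---|---|
| 34/100 | 24.8% |
| 35/100 | 25.7% |
| 31/90 | 24.7% |
| 32/90 | 25.7% |

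At least 35 of 100, or 32 of 90, are needed. With 90 subjects, the two whole counts nearest 35% fall on opposite sides of 25%.

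**Step 3: probability of reaching the cut-off.**

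| True ORR | n = 100 (35 or more) | n = 90 (32 or more) |
|---|---|---|
| 35% | 53.8% | 49.6% |
| 40% | 87.0% | 83.3% |

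A probability of 80% requires a true ORR of 38.6% with 100 subjects or 39.3% with 90.

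**Step 4: lost subjects kept in the denominator.** Suppose the 35% applies only to the 90% who are followed, and the rest count as non-responders among 100. The effective rate is then 0.9 × 35% = 31.5%, and P(X ≥ 35 | 100, 0.315) = 25.7%. The documents do not say whether the 35% already allows for this, so it is a sensitivity case.

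**Step 5: other interval methods.** The Wald interval gives the same cut-offs and probabilities. The Wilson interval, which is not the planned one, gives 62.0% at n = 100 and 58.3% at n = 90.

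**Step 6: Cohort B for comparison.** P(X ≥ 6 | 40, 0.20) = 83.9%, so that statement is correct as a probability.

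**The case against.** The strongest defence is that this is a precision statement in an estimation study. The plan has no efficacy hypothesis, labels its analyses exploratory and reports an ORR with an exact interval. Sizing such a cohort by the interval expected at the assumed rate is common practice, and on that reading the figure reproduces. The probability given for Cohort B may be only a difference in style.

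Much of this stands. A reader might infer an arithmetic error, but no stated number is wrong. A reader might also infer that the cohorts are too small, but the plan states no power for them and no success rule for A-CD, so no stated requirement is missed.

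The defence does not rescue the wording. The sentence speaks of an assumed rate and presents the result as assured, and under its own 10% loss the expected count is not a whole number. The 25% figure also has a role elsewhere, since the futility rule is built on claiming an ORR above it. That link is limited: the rule concerns Cohort A-ID, and Protocol 9.5 records that the analysis was done and the boundary not crossed.

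Another tempting inference is that a lower limit at or below 25% would count against a true ORR of 35%. No section says so, and the intervals do not support it: 34/100 gives 24.8% to 44.2% and 30/100 gives 21.2% to 40.0%, and both contain 35%.

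Finally, one could point to the 42% ORR under continuous dosing cited in Protocol 1.2.1; at a true ORR of 42%, the probability with 100 subjects is 93.7%. But that rate is for a different drug, in 59 subjects, and the plan's planning rate is 35%.

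**Conclusion.** The point holds as an unstated probability presented as an assured property. At a true ORR of 35%, the planned exact interval has a lower limit above 25% in 53.8% of trials with 100 evaluable subjects and 49.6% with 90. These figures assume a two-sided 95% Clopper-Pearson interval, independent responses, and a 35% rate that applies to everyone in the denominator. If the 35% excludes lost subjects who are then counted as non-responders, the figure is about 26%. That case rests on an assumption the documents neither state nor rule out, so it should not be quoted as the design's probability.

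The consequence is moderate. The endpoint, interval method and analysis are unaffected, and the exploratory label limits what depends on the 25% mark. But the sentence is the sole numerical basis for both 100-subject cohorts and should say what the design delivers.

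**What to change.** Replace the sentence in Protocol 9.2, the synopsis and SAP 3.2 with:

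> If 35 of 100 subjects respond, the exact 95% CI is 25.7% to 45.2%. The lower limit exceeds 25% if at least 35 of 100 (or 32 of 90, after 10% loss) respond. The probability of this is 54% (50% with 90 subjects) if the true ORR is 35% and 87% (83%) if it is 40%; a true ORR of about 39% gives 80%.

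Add one sentence saying whether the 35% already counts lost subjects as non-responders, because the primary analysis keeps subjects without an adequate response assessment in the denominator. If it does not, give the resulting probability (about 26%) as well.

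The cost is a few lines in the SAP and in the next protocol amendment, and a published figure that looks less favourable. The number of subjects, the endpoint and the analysis stay as they are.

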9.3. Level of Significance

All CIs provided will be at the 95% confidence level.

9.4. Statistical Analyses

9.4.1. Efficacy Analyses

9.4.1.1. Primary Efficacy Analyses

The primary endpoint of the study is ORR in subjects with FGFR3 mutations or fusions based on the central genomics laboratory results and on a continuous dose regimen, defined as the proportion of subjects with best response (complete response or partial response) by RECIST v1.1 as assessed by a centralized radiological review committee. This analysis will be based on efficacy evaluable population. Subjects who do not have sufficient baseline or on-study response assessment information to be adequately assessed for response status will be included in the denominators in the calculation of ORR. The 95% CI for ORR based on exact method for binomial distribution will be calculated.

Objective response rate will also be analyzed based on per-protocol population as sensitivity analysis.

9.4.1.2. Secondary Efficacy Analyses

[figure not shown]
Secondary efficacy analyses will be conducted for the efficacy evaluable population.

Objective response rate for subjects in Cohort A-ID, for subjects in Cohorts A-CD and A-ID combined; for subjects in Cohorts A-ID, A-CD, and B combined; and for subjects in Cohort B will be analyzed in the same fashion as the primary analysis.

Progression-free survival is defined as number of days from the first day of taking study drug dose to the earlier of death or disease progression by RECIST v1.1 as assessed by the centralized radiological review committee. Progression-free survival data will be analyzed by the Kaplan-Meier method for Cohort A-ID, Cohort A-CD, and Cohort B, separately.

Overall survival is defined as the number of days from the first day taking study drug dose to death due to any cause. Subjects without death observed at the time of the analysis will be censored at last date known to be alive. Overall survival will be analyzed by the Kaplan-Meier method for Cohort A-ID, Cohort A-CD, and Cohort B, separately.

The DOR is defined as the number of days from the date of the first confirmed response to the

9.4.2.1. Adverse Events

A TEAE is any AE either reported for the first time or worsening of a pre-existing event after the first dose of study drug. Analysis of AEs will be limited to TEAEs, but data listings will include all AEs regardless of their timing to study drug administration. Adverse events will be tabulated by the MedDRA preferred term and system organ class. Severity of AEs will be based on CTCAE v4.03 (NCI 2010) using Grades 1 through 4 (see Section 8.1.2 for guidance).

The subset of AEs considered by the investigator to have a relationship to study drug will be considered to be treatment-related AEs. If the investigator does not specify the relationship of the AE to study drug, the AE will be considered treatment-related. The incidence of AEs and treatment-related AEs will be tabulated.

9.4.2.2. Clinical Laboratory Tests

Laboratory test values outside the normal range will be assessed for severity based on the normal ranges for the clinical reference laboratory. The incidence of abnormal laboratory values and shift tables relative to baseline will be tabulated.

Laboratory data will be classified into Grades 1 through 4 using CTCAE v4.03. The following summaries will be produced for the laboratory data:

- Number and percentage of subjects with worst postbaseline CTCAE grade (regardless of baseline value). Each subject will be counted only for the worst grade observed postbaseline.
- Shift tables from baseline to the worst postbaseline value using CTCAE grade.
- For laboratory parameters where CTCAE grades are not defined, shift tables to the worst postbaseline value using the low/normal/high classifications based on laboratory reference ranges.

9.4.2.3. Vital Signs

Descriptive statistics and mean change from baseline will be determined for vital signs (blood pressure, pulse, respiratory rate, and body temperature) at each assessment time. Vital sign results will be reviewed for clinically notable abnormalities (see [Table 9](#)), and subjects exhibiting clinically notable vital sign abnormalities will be listed. A value will be considered an "alert" value if it is outside the established range and shows a > 25% change from baseline.

Table 9: Criteria for Clinically Notable Vital Sign Abnormalities

Parameter	High Threshold	Low Threshold
Systolic blood pressure	> 155 mmHg	< 85 mmHg
Diastolic blood pressure	> 100 mmHg	< 40 mmHg
Pulse	> 100 bpm	< 45 bpm
Temperature	> 38°C	< 35.5°C
Respiratory rate	> 24/min	< 8/min

